8.3. Packaging and Labeling Interview Responses

The packaging and labeling interview will be administered at the Screening/Baseline Visit (Visit 1) to the subset of subjects who were selected to undergo gynecological exams prior to and following tampon use. The number and percentage of subjects that were able to correctly identify and distinguish key product information will be reported for the subset of subjects in the ITT population who undergo gynecological examinations and complete the packaging and labeling interview. A subject will be considered to have correctly identified the information if they: 1)

AD-ST-33.06 Effective date: 12-Nov-2020

correctly identify the key product information in their first response, or 2) correctly identify the information after a follow-up question from the interviewer. The summary will be presented for the subset of subjects in the ITT population overall, not by absorbency arm. The denominator for the percentage calculation will be based upon the total number of subjects in the ITT population who belong to the subset of subjects that were selected to undergo gynecological exams and complete the packaging and labeling interview.

8.4. Product Tolerability

Product tolerability will be evaluated through gynecological exam findings and frequency and severity of adverse events. The analysis of adverse events is presented in Section 9.1 and the analysis of gynecological exam findings is presented in Section 9.5.

9. Safety and Tolerability Analysis

Safety and tolerability will be evaluated from reported adverse events (AEs) and gynecological exam findings. All safety analyses will be performed on the Safety population. Analyses will be performed separately for each absorbency arm.

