## **7 SUBJECT POPULATION**

The study population consists of 2 arms of approximately 369 females (total 738 subjects), ages 18-49, in good general health, in the United States who normally use tampons for menstrual protection, menstruate regularly, and do not have a history of Toxic Shock Syndrome (TSS). One arm will test regular absorbency tampons and the other will test super absorbency tampons. Within each of these arms, a subset of 60 subjects will undergo gynecological exams before and after product use.

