## 8 STUDY CONDUCT AND PROCEDURES

Subjects will be assigned to one of two arms in the study: a regular absorbency arm or a super absorbency arm. Subjects will be assigned to the regular or super absorbency arm based on the tampon absorbency they use most often. Within each arm, a subset of 60 subjects will undergo gynecological exams prior to and following tampon use.

Subjects will be randomly assigned the order in which to test a new tampon design (test tampon) and a currently marketed tampon (reference tampon). Each tampon type will be used over the course of one (1) menstrual cycle. Subjects will be provided with 16 tampons per menstrual cycle.

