#### **Exam Procedures**

A subset of 60 subjects in each arm will undergo a gynecological examination at each visit. Gynecological exams may also be conducted as needed for any subject to assess adverse events.

The following will be included in the exam:

- Symptom assessment

Prior to the vaginal exam, subjects will be asked to complete a short questionnaire regarding vaginal symptoms they may be experiencing. The purpose of this assessment is to alert the clinician of any possible conditions that may need to be addressed for the health of the subject and that may affect eligibility.

- Visual assessment

This gynecological exam will consist of a visual inspection of the perineum, vulva, urethra, vagina, and cervix. Use of a clear speculum and light are expected for this exam. Each anatomical location will be evaluated for lesions. Each lesion will be characterized according to one of the following types:

Type	Epithelium	Blood Vessel	Description	Coverage	Comment
A	Intact	Intact	 Erythema  Edema	 ≤ 50%  > 50%	Provide specific location and any other relevant findings
B	Intact	Disrupted	 Petechia  Ecchymoses	 ≤ 50%  > 50%	
C	 Disrupted, superficial  Disrupted, deep	 Intact  Disrupted	 Peeling  Abrasion  Ulceration  Laceration	 ≤ 50%  > 50%	
D	N/A	N/A	 Other	 ≤ 50%  > 50%	Provide description of the lesion, specific location, and any other relevant findings

Type D lesions can be other lesions not related to epithelial or blood vessel disruption such as cysts, polyps, neoplasms, etc.

Subjects with presence of any Types B or C lesions at baseline will be excluded from the study. Subjects with a Type A lesion (erythema or edema) may be included as long as the coverage area is ≤ 50%. Subjects with Type D lesions will be excluded at the discretion of the investigator.

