Superficial epithelial disruption does not penetrate into the subepithelial tissue. Deep epithelial disruption penetrates into and exposes the subepithelial tissue and possibly blood vessels. If bleeding from the finding is present, the disruption should be recorded as deep.

Lesions identified after the screening visit will be considered adverse events. Severity is determined by disruption of the epithelium and blood vessels. Lesions with an intact epithelium and intact blood vessels are considered mild (Types A). Any lesion that has a deep disruption in the epithelium is considered severe (Type C with deep epithelial disruption). All others are considered moderate (Type B and Type C with superficial epithelial disruption). Severity of “Other” (Type D) lesions will be determined by the Investigator.

- Vaginal discharge

The quantity, odor, color, and consistency of the vaginal discharge will be assessed during the vaginal exam by the investigator to determine whether a vaginal infection is suspected.

- Vaginal pH

Vaginal pH measurements should be taken using pH testing strips and instructions provided. The testing strips measure pH in increments of 0.5, with a minimum range of 4.5 – 7.5.

- Suspected infection

A subject who has symptoms of a vaginal infection or urinary tract infection at screening is not eligible to participate in the study. If a subject develops a vaginal infection or UTI during the study, she will stop using the study product and switch to menstrual pads.

The subject may be treated by the investigator or referred for treatment at the discretion of the investigator. Subjects may continue using study product after treatment is complete and symptoms have resolved, if appropriate for the study design. Development of vaginal infections after screening are recorded and analyzed as adverse events.

- Other abnormal findings

Any other abnormal findings during the vaginal examination will be recorded. Subjects may be excluded for abnormal findings. Abnormal findings recorded after the screening visit will be recorded and analyzed as adverse events.

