#### **Recording Adverse Events**

Adverse events spontaneously reported by the subject and/or in response to an open question from the study personnel or revealed by observation will be recorded during the study at the investigational site. Information about AEs will be collected from the Test Article Dispensation until the end of the study. Serious Adverse Event information will be collected from Test Article Dispensation until 7 days following Visit 4 (Post-use Visit). The AE term should be reported in standard medical terminology when possible. For each AE, the investigator will evaluate and report the onset (date and time), resolution (date and time), intensity, frequency, relationship to test article, action taken, serious outcome (if applicable), and whether or not it caused the subject to discontinue the study.

Intensity will be assessed according to the following scale:

- Mild (awareness of sign or symptom, but easily tolerated)
- Moderate (discomfort sufficient to cause interference with normal activities)
- Severe (incapacitating, with inability to perform normal activities)

It is important to distinguish between serious and severe AEs. An AE of severe intensity may not be considered serious.

Relationship to test article will be assessed according to the following scale:

- Not Related - A clearly evident relationship to other etiologies exists and/or the event is not temporally consistent with test article use.
- Unlikely - Based upon available information, a causal relationship to test article is improbable. Usually, another cause is most plausible.
- Possible - Event follows a reasonable temporal association with test article use and is clinically/biological plausible. Other etiologies are also possible.
- Probable - A reasonable temporal sequence of the event with test article use exists and based upon the medical professional's clinical experience, the association of the event with test article seems very likely.

- Definite - Event is clearly related to article use. It is temporally associated with test article use, follows a known or expected response pattern, and improves when stopping test. Other causes do not appear to explain the event.

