14.3.1 Displays of Adverse Events		
Table 14.3.1.1	Safety	Overall Summary of Adverse Events
Table 14.3.1.2	Safety	Adverse Events by System Organ Class and Preferred Term
Table 14.3.1.3	Safety	Adverse Events by System Organ Class, Preferred Term, and Maximum Severity

Table Number	Population	Table Title / Summary
Table 14.3.1.4	Safety	Adverse Events by System Organ Class, Preferred Term, and Maximum Relationship to Study Product
Table 14.3.1.5	Safety	Adverse Events by System Organ Class, Preferred Term, and Maximum Frequency

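### Adverse events found by gynecological exam are sought in 60 women per arm but divided by the whole Safety population, and two unreconciled severity scales feed one table

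*SAP*

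**What the plan says.** **Who is examined.** Protocol Section 7: "The study population consists of 2 arms of approximately 369 females (total 738 subjects". Protocol Section 8: "Within each arm, a subset of 60 subjects will undergo gynecological exams prior to and following tampon use"; under Exam Procedures, "A subset of 60 subjects in each arm will undergo a gynecological examination at each visit". The same subsection lets any subject be examined as needed to assess an AE.

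**What becomes an AE.** Protocol Exam Procedures: "Lesions identified after the screening visit will be considered adverse events". Vaginal infections that develop after screening and other abnormal exam findings are also recorded and analyzed as AEs.

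**Denominators.** SAP Section 9: "All safety analyses will be performed on the Safety population". The Safety population is every randomized woman who inserts at least one tampon, examined or not. The shell notes for Tables 14.3.1.1 to 14.3.1.5 take percentages over that population within the absorbency group. SAP Section 9.5 and the shells for Tables 14.3.6.1.1 and 14.3.6.1.2 instead use the exam subset of the Safety population.

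**Severity.** Protocol Exam Procedures grades lesions by tissue: Type A is mild, Type B and superficial Type C are moderate, and "Any lesion that has a deep disruption in the epithelium is considered severe". Type D is left to the investigator. Protocol Section 12 (Recording Adverse Events) asks for the intensity of each AE on a functional scale whose top grade is "Severe (incapacitating, with inability to perform normal activities". SAP Table 14.3.1.3 is titled "Adverse Events by System Organ Class, Preferred Term, and Maximum Severity" and has a single set of mild, moderate and severe rows.

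**The concern.** A lesion without symptoms can be found only by looking. About 84% of each arm has no scheduled exam, yet those women stand in the denominator of every AE percentage, so an exam-detected AE looks rarer there than it is among the women in whom it was sought.

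Absolute rates matter in this plan. Tolerability is a validation criterion without a numerical or comparative threshold: it is judged acceptable or not on review of the results, and AE frequency and severity is one of its two named measures. A low lesion percentage, or an empty severe row, may reassure more than the exam data allow.

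The severity rows have a second problem. A deep lesion without symptoms is severe on the tissue scale and at most mild on the functional one. A count that mixes the two has no single meaning.

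**Working it through.** **Inputs.** 369 women per arm (Protocol Sections 7 and 11), 60 with scheduled exams (Protocol Section 8), and all women in the arm as AE denominator (SAP Section 9 and shell notes).

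**The plan's own figure.** The plan states no lesion rate. The 369 can be reproduced from Protocol Section 11 (0.7% versus 0.2%, 80% power, two-sided 0.05, 7 usable tampons per cycle) with the arcsine formula: h = 2·asin(√0.007) − 2·asin(√0.002) = 0.0781; n = 2(1.960 + 0.842)²/h² = 2,577 tampons per type; 2,577/7 = 368.1, rounded up to 369; 369 × 7 = 2,583, as the protocol says.

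**Ceiling.** The share examined is 60/369 = 16.3%. If no lesion is found outside the subset, the factor is 369/60 = 6.15 (738/120 gives the same). With illustrative lesion rates:

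| Lesion rate in examined women | Count | Printed in AE table |
|---|---|---|
| 5% | 3/60 | 3/369 = 0.8% |
| 10% | 6/60 | 6/369 = 1.6% |
| 20% | 12/60 | 12/369 = 3.3% |

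**Detection outside the subset.** Let f be the share of lesions in unexamined women that still surface through symptoms or as-needed exams. The documents give no value, so f is an assumption. Factor = 369/(60 + 309f):

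| f | 0 | 5% | 10% | 25% | 50% |
|---|---|---|---|---|---|
| Factor | 6.15 | 4.9 | 4.1 | 2.7 | 1.7 |

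**Smaller Safety population.** With all 60 examined women kept and f = 0, a Safety population of 300, 330 or 350 gives 5.0, 5.5 or 5.8.

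**Row for at least one AE.** Let b be the background rate of other AEs and r the lesion rate, taken as independent, with f = 0. Subset rate = 1 − (1 − b)(1 − r); all-Safety rate = (60 × subset rate + 309b)/369.
- b = 5%, r = 20%: 24.0% against 8.1%, ratio 3.0.
- b = 20%, r = 10%: 28.0% against 21.3%, ratio 1.3.

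This row is diluted much less than a lesion row.

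**Empty severe row.** Zero of 60 has a one-sided 95% upper bound of 1 − 0.05^(1/60) = 4.9%. Read as zero of 369, it would be 1 − 0.05^(1/369) = 0.8%. The AE shells print no bounds; this shows only what an empty row can support.

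**What the exam tables add.** Table 14.3.6.1.1 gives lesion type and, for Type C, epithelial depth, by body area, visit and tampon type, over the subset. It has no row for a lesion at any site, no relationship to product, and nothing that separates a new post-use lesion from one already present before use. Table 14.3.6.1.2 covers discharge, pH, suspected infection and other findings, also without relationship.

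**Severity scales.** The lesion rule sits in Exam Procedures. The functional scale in Recording Adverse Events covers each AE and makes no exception for lesions. Neither refers to the other, and SAP Section 9.1 sets no rule for combining them.

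**The case against.** The strongest reply is that the tolerability review does not depend on the AE tables alone. SAP Section 8.4 names exam findings as well as AEs, and Section 9.5 narrows the general sentence on the Safety population by using the exam subset. Because the protocol fixes severity by lesion type and depth for Types A to C, most of it can be read from Table 14.3.6.1.1 over the right denominator. Its note also lists the subjects with lesions, and Table 14.1.1 prints the size of the exam subset within the Safety population. This stands. A reader might infer that exam-detected injury looks six times rarer in the report as a whole, or that the exam tables carry no severity information; the documents support neither.

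Three further points stand in whole or part.
- Sixfold is a ceiling, since as-needed exams are allowed in any subject. Symptomatic infections in particular can surface without a scheduled exam and are diluted less.
- A reader might infer that the product comparison is biased. In this crossover the test and reference columns are diluted about equally, so their ratio is largely preserved.
- The lesion-specific severity rule may be meant to override the general scale. That is a reasonable reading, but the protocol does not say so, and even then Table 14.3.1.3 would pool tissue grades with functional grades.

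The reply does not reach relationship to product or a woman's overall lesion severity across sites. Those are tabulated only in the AE tables, on the diluted denominator.

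**Conclusion.** The concern holds in a limited form. In Tables 14.3.1.1 to 14.3.1.5, rates of exam-detected AEs are understated by up to 6.15-fold, and by 4.1-fold or 2.7-fold if 10% or 25% of lesions in unexamined women are found. The row for at least one AE is affected less (1.3- to 3.0-fold under the assumed rates). The distortion concerns absolute AE percentages; exam findings on the correct denominator are not lost to the report.

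The figures assume full enrolment, all women in the Safety population unless stated otherwise, and the same lesion incidence in examined and unexamined women. The design and randomization sections do not say how the subset is chosen, so the last assumption cannot be checked.

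The severity conflict is a separate defect: two scales, no stated precedence, one set of rows. It is worth correcting before the tables are produced because AE frequency and severity is a named tolerability measure judged without a threshold.

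**What to change.** 1. Repeat at least Tables 14.3.1.1, 14.3.1.3 and 14.3.1.4 for the gynecological exam subset. The denominator for each product column is the women scheduled for exams who used that product.
2. Footnote the all-subject AE tables: asymptomatic lesions were sought only in the exam subset, so these percentages are not lesion rates for the arm.
3. Reconcile Protocol Exam Procedures with Recording Adverse Events so that one stated severity scale applies to lesion AEs, and carry that statement into SAP Section 9.1. Tabulate lesion severity apart from functional intensity.

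**Cost.** A few repeated shells, one footnote and a short clarification in each document. Item 3 needs lesion AEs to be identified, probably by linking AE and exam records, since AE Listing 16.2.7.1 has no field for how an event was found. Printed lesion rates will look less favourable. No new data and no extra subjects are needed.

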9.1. Adverse Events

All AEs and serious adverse events (SAEs) will be coded using the MedDRA v. 25.1.

All AE data will be summarized for 3 periods: before any test article use, during and following test tampon use, during and following reference tampon use. AEs will be assigned to an analysis period based on the below criteria. The criteria for assigning AEs to an analysis period will differ depending on the type of test article (reference or test tampon) first used by the subject.

Test article order	Criteria for assigning AEs to analysis periods
Reference tampon → Test tampon	If the start date of the adverse event was before the date of first insertion of a reference tampon, then the AE will be assigned to the “before any test article use” period. If the start date of the adverse event was on or after the date of first insertion of a reference tampon, but before the date of first insertion of a test tampon, then the adverse event will be assigned to the “during and following reference tampon use” period. If the start date of the adverse event was on or after the date of first insertion of a test tampon, then the adverse event will be assigned to the “during and following test tampon use” period.

Test tampon → Reference tampon	
If the start date of the adverse event was before the date of first insertion of a test tampon, then the AE will be assigned to the “before any test article use” period.
 
If the start date of the adverse event was on or after the date of first insertion of a test tampon, but before the date of first insertion of a reference tampon, then the adverse event will be assigned to the “during and following test tampon use” period.
 
If the start date of the adverse event was on or after the date of first insertion of a reference tampon, then the adverse event will be assigned to the “during and following reference tampon use” period.

--------------------------------	--

An overall summary of AEs will be provided; this will present number and percentage of subjects who reported at least 1 of the following: any AE, AEs by maximum severity, AEs by maximum relationship to study product, AEs by maximum frequency, and SAEs.

In addition to the overall summary, summaries of the number and percentage of subjects with AEs will be displayed for each absorbency arm, grouped by MedDRA system organ class and preferred term (coded using MedDRA v. 25.1). Summaries of AEs by severity, relationship to study product, and frequency will also be provided. In the case of multiple occurrences of the same AE within the same subject, each subject will only be counted once for each preferred term.

In the summaries showing severity, relationship to study product, and frequency, the event with the maximum severity, strongest relationship, and highest frequency, respectively, will be reported. If a particular event is missing the severity, relationship, or frequency then the strongest possible severity, relationship, or frequency will be assumed for analysis (severity = severe, relationship = definitely related, frequency = continuous).

A data listing of all AEs will be provided, displaying details of the event(s) captured on the CRF.

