### **Subject Inclusion Criteria**

Women who meet all the following inclusion criteria will be eligible for participation in the study:

1. Willing and able to read and provide written informed consent.
2. Female in good general health, age 18-49 (inclusive).
3. Last pap smear was normal in the past 3 years, or a normal pap with a negative HPV in the past 5 years, or negative HPV in the last five years (age <21 does NOT need a PAP or HPV result) based on self-report
4. History of regular menstrual cycles during the previous 3 months lasting approximately 21-35 days, including at least 4 days of menstruation, and expecting to menstruate during the study period.
5. Tracks menstruation and able to confidently predict onset of menstruation within 72 hours.
6. History of use of applicator tampons without discomfort.
7. Normally use at least 6 tampons for protection during menstruation.
8. Normally uses regular, super, and/or super plus absorbency tampons for menstrual protection.

9. If uses super plus absorbency, must be willing to wear nothing greater than super absorbency for the duration of the study.
10. Agrees not to use douching substances, vaginal medications, suppositories, or vaginal devices for the duration of the study.
11. **[For subjects undergoing gynecological exams only]** Agrees not to apply feminine deodorant spray, powders, perfumes, wipes, lotions, creams or emollients to the genital area for at least 24 hours prior to each visit.
12. Agrees not to try any new products in the vaginal/perineal area two (2) weeks prior to the study start and for the duration of the study.
13. Agrees to the conduct of all study procedures, including gynecological exams (if applicable), and agrees to follow all study instructions and return for scheduled appointments.
14. Has used an acceptable form of birth control for at least one month prior to enrollment and for the duration of the study. Acceptable methods include hormonal contraceptive, IUD, tubal ligation, partner vasectomy, condom (with or without spermicide), or abstinence.

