#### **Randomization**

Subjects will be assigned a unique subject identification number by the site at screening. Following completion of the screening procedures, eligible subjects will be assigned to either the regular or super absorbency arm, based on the tampon absorbency the subject uses most often. Within each arm, the order in which the test and reference tampons will be used will be randomized.

A randomization schedule that was created by the unblinded biostatistician at [REDACTED] will be provided to each site. Unique subject randomization numbers will be assigned by the site according to the site specific randomization schedule. Randomization numbers should be assigned sequentially within each arm.

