## 10 STUDY VISIT SCHEDULE

Subjects will be assigned to one of two arms in the study: a regular absorbency arm or a super absorbency arm. Within each arm, a subset of 60 subjects (Subset Population) will undergo gynecological exams prior to and following tampon use. The study visit schedule is the same for both arms of the study.

For subjects in the Subset Population, the study will consist of 4 visits for each study subject, 2 visits for each menstrual cycle: one before and after each menstrual cycle.

For all other subjects, the study will consist of 3 visits: a screening and pre-use visit, and two post-use visits.

Pre-use visits will be conducted within 72 hours prior to expected menstruation. Post-use visits are to be completed within 72 hours following the last tampon use for that menstrual cycle.

The schedule of visits and timing of procedures are summarized in the Proposed Schedule of Events (Table 1 - Proposed Schedule of Events).

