3.1. Overall Design

This study is an open-label, randomized, crossover study designed to validate that changes to the design of [REDACTED] tampons meet defined user needs. Subjects will be assigned to either a regular absorbency arm or super absorbency arm. Subjects will test a new tampon design (test tampon) and a commercially available tampon design (reference tampon).

Each tampon type will be used over the course of one menstrual cycle. Within each absorbency arm, subjects will be randomized to the order in which to use the test tampon and the reference tampon. Subject participation in the study will last over the course of 2 menstrual cycles, or approximately 2 months.

A subset of 120 subjects (60 subjects within each absorbency arm) will undergo gynecological examinations prior to and following tampon use. For the subset of subjects undergoing gynecological exams, the study will include a total of 4 visits, 2 visits for each menstrual cycle. The first visit will be the screening visit and the first pre-use visit. The next visit will be the first post-use visit, followed by the second pre-use visit and the second post-use visit. Pre-use visits will be conducted within 72 hours prior to expected menstruation and post-use visits will be conducted within 72 hours following the last tampon use for that menstrual cycle. Gynecological examinations will be performed at each visit. This subset of subjects will also complete a packaging and labeling interview at the first visit to assess whether subjects can identify and distinguish key information on the product packaging.

For the remainder of subjects who will not undergo gynecological examinations, the study will include 3 visits: a screening/pre-use visit and 2 post-use visits. Post-use visits will be conducted within 72 hours following the last tampon use for that menstrual cycle.

All subjects will keep a diary during menstruation with entries for each tampon used and will collect each used tampon to be returned to the site. At each post-use visit, site personnel will review subject diaries for completeness and accuracy, record the number of used and unused tampons returned, and evaluate used tampons to assess tampon integrity. Subjects will be considered to have completed the study after they complete the second post-use visit. Refer to the Schedule of Events (Table 1) for more details.

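### SAP 9.1 observes the product used first for a whole cycle but the product used second only to Visit 4 (non-serious AEs): the AE columns are diluted, though not biased, and need a matched-window split

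*SAP*

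**What the plan says.** SAP 9.1 sorts AEs into three periods: before any product, and *during and following* each of the two products. In reference-first women, an onset "on or after the date of first insertion of a reference tampon, but before the date of first insertion of a test tampon" goes to the reference tampon. An onset "on or after the date of first insertion of a test tampon, then the adverse event will be assigned" to the test tampon. Test-first women follow the mirror rule. The SAP sets no closing date for the second window, so it ends when collection ends:

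- Protocol 12, Recording Adverse Events: "Information about AEs will be collected from the Test Article Dispensation until the end of the study". Serious events are collected for a further 7 days after Visit 4.
- SAP 3.1: "Subjects will be considered to have completed the study after they complete the second post-use visit".
- Protocol 10: "Post-use visits are to be completed within 72 hours following the last tampon use for that menstrual cycle".

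Eligible women have cycles "lasting approximately 21-35 days, including at least 4 days of menstruation" (Protocol 7, inclusion criterion 4).

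In the exam subset (60 women per arm), Visit 3 takes place in the 72 hours before the second expected menstruation. Protocol 8, Exam Procedures, counts new lesions, infections and other abnormal findings after screening as AEs.

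The AE shells (Tables 14.3.1.1 to 14.3.1.5 and 14.3.2.1) have one column per product. Both orders are pooled and results are percentages of women. There is no subject-time denominator and no split by period or sequence.

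**The concern.** The length of a product's AE window depends on whether it was used first or second. A product used first collects everything that happens over the rest of the cycle, most of it after the last tampon. A product used second collects little beyond its days of use.

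In the exam subset, Visits 2 and 3 both normally fall in the first product's window and only Visit 4 falls in the second's. A lesion first seen at Visit 3 is charged to a product last used weeks earlier.

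AE frequency and severity are one of the two tolerability measures (SAP 8.4), and acceptable tolerability is a validation criterion judged on review of the results. Columns loaded with events unrelated to use make a real difference between products harder to see.

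**Working it through.** The plan states no length for either window, so there is no figure to reproduce.

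**Inputs**
- From the documents: cycle 21–35 days (midpoint 28), menstruation of at least 4 days, post-use visit 0–3 days after the last tampon, SAE collection to Visit 4 + 7 days.
- Assumed: 5 days of use (range 4–7), 1:1 order (the ratio is not stated), and product 2 starting one cycle after product 1.

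**Window lengths** (window 1 = cycle; window 2 = days of use + visit lag, plus 7 for SAEs)

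| | Central case | Range |
|---|---|---|
| Window 1 | 28 days | 21–35 |
| Window 2, non-serious | 5 + 3 = 8 days | 4–10 |
| Ratio, non-serious | 28/8 = 3.5 | 21/10 = 2.1 to 35/4 = 8.8 |
| Window 2, SAE | 8 + 7 = 15 days | 11–17 |
| Ratio, SAE | 28/15 = 1.9 | 21/17 = 1.2 to 35/11 = 3.2 |

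**Tampon-free share (non-serious AEs).** Window 1: (28 − 5)/28 = 82%. Window 2: 3/8 = 38%. Pooled column: (23 + 3)/(28 + 8) = 72%, range 50–81%. If both windows ended at the post-use visit, the share would be 3/8 = 38% in each.

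**Gap from last tampon to Visit 3.** 28 − 5 − (0 to 3) = 20–23 days. Over the range it runs from 21 − 7 − 3 = 11 to 35 − 4 = 31 days.

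**Is one product favoured?** Take an assumed background of 0.003 AEs per woman-day. The chance of at least one AE is 1 − exp(−0.003 × 28) = 8.1% in a first window and 1 − exp(−0.003 × 8) = 2.4% in a second. With 1:1 order each product column averages 5.2%, a ratio of 1.00. The ratio would be 1.12 if 55% of women used the test tampon first and 1.25 if 60% did; the documents suggest neither split.

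**Dilution.** Model the risk as use-related risk + b × days. The pooled column averages (28 + 8)/2 = 18 days and the matched window is 8 days. Assumed use-related risks are 6% and 3%.

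| b per day | SAP windows | Matched windows |
|---|---|---|
| 0.002 | 9.6% / 6.6% = 1.45 | 7.6% / 4.6% = 1.65 |
| 0.004 | 13.2% / 10.2% = 1.29 | 9.2% / 6.2% = 1.48 |

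The difference is 3 points in every cell. Its standard error is proportional to the square root of the summed p(1 − p), treating the columns as independent with equal denominators:
- b = 0.002: √(0.1484/0.1141) = 1.14
- b = 0.004: √(0.2062/0.1417) = 1.21

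The SAP windows therefore make the same difference 14–21% noisier.

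A second illustration needs no background figure. If one product doubled the event rate on 5 days of use, the expected event ratio would be (18 + 5)/18 = 1.28 under the SAP rule and (8 + 5)/8 = 1.63 in matched windows.

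**The case against.** Much of the case for leaving the rule alone is sound.

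- **Randomized order.** Both products get both windows equally in expectation, so the rule does not tilt the comparison. This stands.
- **Subset imbalance.** Protocol 8 says "Randomization numbers should be assigned sequentially within each arm" and describes no separate list for the exam subset. A reader might infer that an uneven order among the 60 exam women produces a sizeable false difference. At 37:23, those women alone would give 37×28 + 23×8 = 1,220 against 23×28 + 37×8 = 940 days. But every AE table uses the whole arm. If the arm of 369 is split 184:185, the columns hold 184×28 + 185×8 = 6,632 and 185×28 + 184×8 = 6,652 days, a ratio of 1.00. If the other 309 women split evenly, the totals are 6,782 and 6,502, a ratio of 1.04. The inference fails for the planned tables, and the documents give no basis for asking for a separate subset randomization list.
- **Other displays.** The relationship tables and the AE listing, with onset dates, help to separate unrelated events. The exam tables (14.3.6.1.1 and 14.3.6.1.2) already compare one pre-use and one post-use exam per product. This helps, but none of these gives AE frequency a matched window.
- **Metric and model.** The risk difference is not diluted, the shells print percentages rather than ratios, the 6%, 3% and background rates are illustrative, and the model places every use-related event before the post-use visit. All true. The loss of precision and the tampon-free days remain.
- **Deliberate follow-up.** The *during and following* label is meant to keep late-onset events with the product. That is a good reason to keep the present allocation visible, but not to make it the only comparison.

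**Conclusion.** The point holds as one of unequal observation time and dilution. For non-serious AEs the first window is about 3.5 times the second (2.1–8.8 over the assumed range); for SAEs it is about 1.9 times. The two-against-one exam count applies to 120 of the 738 women only. Tampon use itself is assumed equal, at 7 per cycle; it is the follow-up that differs.

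A reader might infer a systematic bias toward one product. The documents do not support that under 1:1 order. Nor does the rule threaten a numeric decision, because tolerability has no threshold and no test-versus-reference rule. What is lost is a like-for-like AE comparison to inform that judgement. The sizes rest on the assumed days of use, the 1:1 order and the illustrative risks; the direction of the window difference does not change anywhere in the range examined.

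**What to change.** In SAP 9.1 and the AE shells, split each product's events into:

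1. a matched window, from that product's first insertion through its own post-use visit (Visit 2 or Visit 4), including findings at that visit;
2. a separate column, *between periods after test* or *between periods after reference*, for onsets after Visit 2 and before the second product's first insertion, including new Visit 3 findings.

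Make the test-versus-reference AE comparison on the matched windows. Keep the current *during and following* allocation displayed alongside, so that late-onset events, and SAEs after Visit 4, stay visible under the product. The wording should also say where the window closes for a woman who misses her post-use visit.

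The cost is SAP wording and extra table columns, with no new data and no event lost. The downside is that late-onset events fall outside the matched column, which is why the present allocation should stay beside it. No change to the randomization is needed.
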